13.2 Laboratory assessments – Marked abnormality criteria

The following criteria will be applied in the determination of marked abnormalities for laboratory assessment values. They are based on Version 5 of the Common Terminology Criteria for Adverse Events (CTCAE) grade 3 or higher criteria unless otherwise noted. If both high and low criteria are shown for a parameter, the criteria should be summarized separately in tabular or graphical data summaries.

13.2.1 Hematology

PARAMETER	UNIT (conventional)	UNIT (standard)	MARKED ABNORMALITY CRITERIA
Hemoglobin	g/dL	g/L	<8.0 g/dL; <80 g/L
WBC (Leukocytes) ¹	10 ⁹ /L	10 ⁹ /L	Low: <2.0 x 10 ⁹ /L High: >30 x 10 ⁹ /L
Lymphocytes Absolute	10 ⁹ /L	10 ⁹ /L	Low: <0.5 x 10 ⁹ /L High: >20 x 10 ⁹ /L
Neutrophils Absolute	10 ⁹ /L	10 ⁹ /L	<1.0 x 10 ⁹ /L
Platelets ²	10 ⁹ /L	10 ⁹ /L	<50.0 x 10 ⁹ /L

¹WBC (Leukocytes) markedly abnormal high criterion is not based on Version 5 CTCAE Grade 3 or higher criteria. Due to the mechanism of action of RLZ, the safety alert is related to infection risk which would be identified by a lower cut-point than the standard which is related to acute leukemias. A markedly abnormal high cut-point >30 x 10⁹/L is applied to flag leukocytosis (George 2012).

²For blinded ITP protocols, Platelets will not be assessed for TEMA because this parameter will be blinded and is expected to be abnormally low due to the participant population and entry criteria.

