6.2.1 Procedures for maintaining and breaking the treatment blind

6.2.1.1 Maintenance of study treatment blind

All study participant treatment details, rozanolixizumab treatment arm, planned dose, or placebo, will be allocated and maintained by the IRT system.

Study site pharmacists or other suitably qualified site personnel who are responsible for preparations of the IMP will be unblinded as they have access to treatment allocations for individual participants via the IRT. The unblinded pharmacy monitors from the contract research organization (CRO), the Clinical Supply Manager, and the unblinded Clinical Project Manager (CPM) (or designee) will also have access to the treatment allocations and to the drug accountability records, if applicable.

The following individuals may, as necessary, have access to the treatment allocations for individual participants via the IRT:

- Sponsor Patient Safety (PS) staff as needed for reporting SAEs to regulatory authorities.
- Members of the IDMC who participate in unblinded sessions will be given information about the IMP allocation for those participants for whom data are provided at these sessions.
- Sponsor and/or CRO staff supporting preparation of the data outputs for the IDMC review and/or any interim analyses.
- A Quantitative Clinical Pharmacologist/Modeling and Simulation Scientist may have access to the randomization code if PK data are requested for review by the IDMC.
- The bioanalytical scientific manager (or designee)

An independent Quantitative Clinical Pharmacologist/Modeling and Simulation Scientist may have access to the randomization code to review unblinded PK, platelet and serum IgG data.

All study participant treatment details will be allocated and maintained by the IRT system.

For safety reasons, the blinded investigator (or designee) has to receive and review the platelet counts from the local laboratory, which will be documented by the blinded site personnel in the eCRF. An increase in platelet count during the Treatment Period is not considered as an unblinding. As such, an increase in platelet count is expected for approximately 60% of the study participants, and up to 10% of placebo-treated study participants may experience an increase in platelet count. Platelet counts may be shared with study participants as this is deemed necessary information for participants when engaging in activities of daily living.

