7.1.4 Temporary IMP discontinuation

Study participant **MUST temporarily discontinue IMP** if any of the following events occur:

1. Thrombocytosis (platelet count of $\geq 400 \times 10^9/L$).

2. In the event of confirmed COVID-19 infection (eg, signs/symptoms such as fever, cough, shortness of breath), or known exposure sufficient to necessitate testing or self-imposed quarantine.

The IMP may be restarted if:

- a. COVID-19 test is negative, and signs and symptoms have resolved
- b. If test is not available, resolution of signs and symptoms and 14 days have passed since initial presentation of the clinical signs/symptoms.
- c. If asymptomatic, 14 days have elapsed since known exposure.

Study participant **MAY temporarily discontinue IMP** if any of the following events occur:

1. A severe AE of headache that is considered related to the IMP in the opinion of the investigator (Section 10.22)
2. A splenectomised study participant develops a (persistent or re-occurring) nonserious infection, as per investigator's decision (Section 10.25)
3. Total serum IgG value is <1g/L as per investigator's decision. As IMP treatment is administered weekly, the decision to temporarily hold the treatment should be determined based on the most recently available total IgG value. As the IgG, IgG subtypes, albumin and total protein levels will be blinded to both the study site personnel and the clinical team at the sponsor and CRO, unblinded Medical Monitors will be monitoring the IgG levels and will alert the investigator in case of decreases <1g/L. Additionally, guidance for investigators on management of infections can be found in Appendix 25, Section 10.25.

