Other Screening Tests	
 • Follicle-stimulating hormone and estradiol (as needed in women of non-childbearing potential only) • Serum or urine human chorionic gonadotropin (hCG) pregnancy test (as needed for women of childbearing potential)^h • Serology (human immunodeficiency [HIV] antibody, hepatitis B surface antigen [HBsAg], and hepatitis C virus antibody) • All study-required laboratory assessments will be performed by a central laboratory except the platelet count which is done by local laboratory. • The results of each test must be entered into the electronic Case Report Form (eCRF). 		

^a Platelet count testing will be performed by a local laboratory. Results will be unblinded to the investigator, site, and study participant (see Section 6.2.1.1).

^b International Normalized Ratio (INR) to be done only at Screening (Visit 1) and for PDILI.

^c Activated partial thromboplastin time (aPTT) and Fibrinogen will be done at all visits which require safety laboratory assessments.

^d Details of liver chemistry stopping criteria and required actions and follow-up assessments after liver stopping or monitoring event are given in Section 7.1.1 and Appendix 6, Section 10.6. All events of ALT $\geq 3x$ upper limit of normal (ULN) and bilirubin $\geq 2x$ ULN (>35% direct bilirubin) or ALT $\geq 3x$ ULN and international normalized ratio (INR) >1.5, if INR measured, may indicate severe liver injury (possible Hy's Law) and must be reported as a serious adverse event (SAE) (excluding studies of hepatic impairment or cirrhosis).

^e Includes total IgG, IgG subclasses, IgA, IgM, and IgE. Results of the IgG testing including the vaccination specific titers will be blinded to the investigator, site, and sponsor for post baseline results.

^f Local urine testing will be standard for the protocol unless serum testing is required by local regulation or Independent Review Board/Independent Ethics Committee.

Investigators must document their review of each laboratory safety report.

Laboratory/analyte results that could unblind the study will not be reported to study sites or other blinded personnel until the study has been unblinded.

10.3 Appendix 3: Adverse events – definitions and procedures for recording, evaluating, follow up, and reporting

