8.3.2 Mean change from Baseline in platelet count by visit

Mean change from Baseline in platelet count will be summarized descriptively using the RS at each timepoint.

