10.5 Clinical Safety Laboratory Assessments

Laboratory data (as specified in Table 10-1 Protocol-required safety laboratory assessments in the protocol) and changes from Baseline (if applicable) for numeric variables will be listed by treatment group and timepoint. Values outside the reference range for the numeric variables will be flagged in the listings. The reference ranges will also be reported in the listings. In addition, the listings will include a flag for values identified as Laboratory assessments – MA Criteria (Appendix 13.2).

Measurements BLQ will be imputed with half of the LLOQ for the purpose of calculating change from Baseline. Measurements ALQ, if applicable, will be imputed to the upper quantification limit. These rules will be applied to all safety laboratory data including clinical chemistry and urinalysis.

Descriptive statistics will be calculated if at most 1/3 of the individual data points at a time point are missing or are either not quantifiable (<LLOQ) or ALQ. Values that are BLQ will be replaced by the numerical value of the LLOQ/2 in this instance and values that are ALQ will be imputed to the value of the upper quantification limit. If more than two-thirds of the individual data points at a timepoint are missing or not quantifiable (BLQ and/or ALQ), no descriptive statistics will be calculated.

The following summaries/tables will be created:

- A summary of participants who meet each of the Laboratory assessments – MA criteria (Appendix Section 13.2) will be summarized by treatment group at each timepoint.

A listing for laboratory assessments will be also created using the SS.

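### SAP 13.2.1 omits platelets from the marked-abnormality assessment partly for a blinding reason that the protocol contradicts; separately, no planned table counts by arm the participants who reach the protocol's hold level of 400×10⁹/L or more

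*SAP*

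**What the plan says.** SAP 10.5 plans a table of participants who meet each laboratory marked-abnormality criterion, which "will be summarized by treatment group at each timepoint". The criteria are in SAP 13.2. For platelets, 13.2.1 has one criterion, a count below 50×10⁹/L, and footnote 2 then takes platelets out of the assessment. It gives two reasons: "Platelets will not be assessed for TEMA because this parameter will be blinded", and the parameter "is expected to be abnormally low due to the participant population and entry criteria".

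The protocol treats platelet counts differently. Table 10-1, footnote a (Appendix 2) says: "Results will be unblinded to the investigator, site, and study participant". Section 6.2.1.1 says that for safety reasons "the blinded investigator (or designee) has to receive and review the platelet counts from the local laboratory", and allows the counts to be shared with participants. Section 7.1.4 puts thrombocytosis, defined as a count of 400×10⁹/L or more, first among the events that require a temporary stop of treatment. Table 1-1 has a stop at the same level.

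Elsewhere the SAP plans one by-arm summary of platelet values over time: "Mean change from Baseline in platelet count will be summarized descriptively using the RS at each timepoint" (8.3.2).

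**The concern.** The drug is given to raise platelets, and the protocol sets an upper safety limit for the count, requires treatment to be held there, and monitors thrombotic and thromboembolic events. How many participants in each arm reached that limit is a natural line in a safety report. The SAP gives no such line, and its stated ground for omitting platelets from the laboratory table includes a statement about blinding that does not fit this trial. At stake are the accuracy of the stated rationale and a simple by-arm count that a reader of the study report would expect.

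**Working it through.** The plan states no figure to reproduce, so this is mainly a comparison of passages.

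**1. Is the blinding reason correct?** No. Protocol Table 10-1 and Section 6.2.1.1 keep the counts open at the site. Blinding would not be a ground for exclusion in any case: protocol 7.1.4 blinds IgG and albumin to the site and to the sponsor and CRO clinical teams, yet SAP 13.2.2 has marked-abnormality rows for both.

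**2. Does the second reason hold?** Yes, for the low criterion. Inclusion criterion 8 requires the average of the Screening and Baseline counts to be below 30×10⁹/L, with neither above 35×10⁹/L. Everyone eligible therefore starts below 50×10⁹/L, and a row for counts below 50 would say little. This reason does not bear on high counts.

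**3. Would deleting footnote 2 give the missing count?** No. The existing criterion is a count below 50; the hold level is 400 or more. The two ranges do not overlap, so the restored row would count nobody at the hold level. The gap comes from the absence of a high criterion. White cells and lymphocytes have both a low and a high one.

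**4. Does another planned table supply the count?**
- SAP 8.3.2 gives descriptive statistics of change by visit, and SAP 3.1 includes the maximum among these. With Baseline at most 35, a count of 400 needs a rise of at least 400 − 35 = 365. If every visit maximum is below 365, no eligible participant reached 400 at a summarized visit. If some are higher, the table does not say how many different participants are involved.
- The adverse event overview (SAP 10.2.2) has a by-arm row for events leading to temporary interruption, but it is not split by cause, and a laboratory value becomes an adverse event only if judged clinically significant (protocol 10.3.1).
- Non-serious events are tabulated only above 5% of participants. The arm sizes are not given. Assuming 22:11 from the 2:1 ratio, one event on rozanolixizumab is 1/22 = 4.5% (1/20 = 5.0% to 1/24 = 4.2% for splits of 20:13 to 24:9), and 1/33 = 3.0% overall. A single case could miss that table.
- The adverse events of focus include thromboembolic events and worsening thrombocytopenia, not thrombocytosis, and 10.2.2 lists them only.

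**5. Where do the values appear?** In listings: efficacy variables by treatment group and visit (SAP 8); laboratory data by treatment group and timepoint with out-of-range flags (10.5); repeated and unscheduled values (4.3); and drug administration with reasons for interruption (10.1).

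**6. Did the rule apply to those analysed?** All 33 were randomized before Amendment 3 (SAP 2.4), under Amendment 2 according to SAP 3.9. The protocol's amendment history places the thrombocytosis item in Section 7.1.4 from Amendment 1.

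**7. How precise would the count be?** Exact (Clopper-Pearson) 95% limits, assuming 22 on rozanolixizumab:
- 0/22: upper limit 1 − 0.025^(1/22) = 15.4%. With 20 or 24 it is 1 − 0.025^(1/20) = 16.8% or 1 − 0.025^(1/24) = 14.2%.
- 1/22 = 4.5%: limits 0.1% to 22.8%.

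**The case against.** The strongest reply is that the exclusion stands on its second reason alone. Footnote 2 removes only a criterion for counts below 50, which is uninformative here. The criteria follow CTCAE Grade 3 or higher unless otherwise noted, so a high platelet limit would be an addition and not the repair of an error. The study was stopped early, and most safety reporting was deliberately cut to listings. Thrombocytosis is not a listed safety endpoint, and the related clinical harm is covered: adverse events of special monitoring, which include thrombotic and thromboembolic events, are in the by-arm overview.

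Much of this stands. The low criterion is rightly dropped, and the missing count is a modest omission. What does not stand is the blinding statement. The SAP also already departs from CTCAE where the programme's safety interest calls for it: a lower cut-point for high white cells, a CRP limit, and an IgG limit tied to the study protocols.

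A reader might infer two stronger points, and the documents support neither. The first is that the mistaken blinding reason causes the missing count; it does not, because the only criterion the footnote removes is a low one. The second is that the report will be unable to say how many participants per arm reached the limit; it can, because individual counts, including unscheduled ones, and reasons for interruption are listed and can be tallied by hand.

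**Conclusion.** Two separate findings hold. First, one of the two reasons in SAP 13.2.1, footnote 2, contradicts the protocol and should go. Second, the SAP has no high platelet criterion, so no planned table gives by arm the number of participants who reached the protocol's own hold level; that information sits only in listings. The consequence is one of presentation: no efficacy result is affected and no data are lost. The count would be imprecise whatever it showed, with the limits above resting on an assumed 2:1 split of 33. The change is worth making because it is cheap and replaces an exclusion resting partly on a wrong premise with one direct count.

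**What to change.** In SAP 13.2.1:
- Delete the blinding reason from footnote 2.
- Limit the footnote to the low criterion: counts below 50×10⁹/L are not tabulated because they are low by eligibility. Deleting the blinding reason without this step would leave platelets excluded altogether.
- Add a high platelet criterion equal to the protocol's existing hold threshold, 400×10⁹/L or more.

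In SAP 10.5, add one table line giving, by treatment group, the number and percentage of Safety Set participants with at least one post-Baseline local count, scheduled or unscheduled, at or above that threshold. It needs its own line because the marked-abnormality summaries are by timepoint.

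The protocol synopsis and SAP 10.1 also describe a stop for counts above 400×10⁹/L, whereas Table 1-1 and Section 7.1.4 include 400 itself; these passages should be reconciled so that the table and the rule use the same limit.

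The cost is one criterion and one table line from data already collected. The drawback is an imprecise percentage, best reported as a count with its denominator.

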13.2.2 Chemistry

PARAMETER	UNIT (conventional)	UNIT (standard)	MARKED ABNORMALITY CRITERIA
AST (SGOT)	U/L	U/L	>5.0 x ULN
ALT (SGPT)	U/L	U/L	>5.0 x ULN
ALP (Alkaline Phosphatase)	U/L	U/L	>5.0 x ULN
GGT (Gamma Glutamyl Transferase) ¹	U/L	U/L	>5.0 x ULN
Bilirubin (Total)	mg/dL	umol/L	>3.0 x ULN if Baseline value is normal; >3.0 x Baseline value if Baseline is abnormal
Albumin	g/dL	g/L	<2 g/dL; <20 g/L
Creatinine	mg/dL	umol/L	>3.0 x ULN
Estimate glomerular filtrate rate (eGFR) ²	mL/min/1.73 m	mL/min/1.73 m	eGFR <29 mL/min/1.73 m
C reactive protein (CRP) ³	mg/L	mg/L	>10mg/L
Corrected Calcium ⁴	mg/dL	mmol/L	Low: Corrected serum calcium of <7.0 mg/dL; <1.75 mmol/L
			High: Corrected serum calcium of >12.5 mg/dL; >3.1 mmol/L
Immunoglobulin G ⁵	(g/L)	(g/L)	≤1 g/L
Potassium	mmol/L	mmol/L	Low: <2.5 mmol/L
			High: >6.0 mmol/L
Sodium	mmol/L	mmol/L	Low: <125 mmol/L
			High: >155 mmol/L
Glucose	mg/dL	mmol/L	Low: <40 mg/dL; <2.2 mmol/L
			High: > 250 mg/dL; >13.9 mmol/L
Total Cholesterol ¹	mg/dL	mmol/L	>400 mg/dL; >10.34 mmol/L
Triglycerides ¹	mg/dL	mmol/L	>500 mg/dL; >5.7 mmol/L

Abbreviations: ALT= alanine aminotransferase; AST = aspartate aminotransferase; dL = deciliter; GGT: gamma-glutamyltransferase; L = liter; mg = milligram; mmol = millimoles; µg = microgram; U = unit; ULN = upper limit of normal

Note: Marked abnormality criteria are defined by Grade 3 or higher events according to the CTCAE, Version 5.0 unless otherwise noted.

¹GGT, Total Cholesterol and Triglycerides were to be collected under Protocol Amendment 3 but were not collected under Protocol Amendment 2. Since no participants were enrolled under Protocol Amendment 3, these laboratory assessments will not summarized or listed.

²eGFR is calculated using the Chronic Kidney Disease Epidemiology Collaboration or CKD-EPI formula (https://qxmd.com/calculate/calculator_251/egfr-using-ckd-epi) which is $eGFR = 141 * \min(\text{Scr}/\kappa, 1)^\alpha * \max(\text{Scr}/\kappa, 1)^{-1.209} * 0.993^{\text{Age}} * 1.018$ [if female] * 1.159 [if black]; where Scr is serum creatinine (mg/dL), κ is 0.7 for females and 0.9 for males, α is -0.329 for females and -0.411 for males, min indicates the minimum of Scr/ κ or 1, and max indicates the maximum of Scr/ κ or 1. For derivation from values in standard units (umol/L) the κ values are 61.9 for females and 79.6 for males.

³Includes CRP and High Sensitivity (HS) CRP. Reference for marked abnormality criteria: Nehring, S.M.; Goyal, A.; Patel, B.C. (2020). StatPearls Publishing, web link: <https://www.ncbi.nlm.nih.gov/books/NBK441843/>. A moderate elevation of CRP level per referred reference is used for the marked abnormality criteria for RLZ to ensure a change suggestive of inflammatory process is captured.

⁴Corrected Calcium = $0.02 * (40 - \text{albumin (g/L)}) + \text{calcium (mmol/L)}$

⁵Immunoglobulin G criterion based on immunodeficiency literature and noted in RLZ study protocols.

⁶Glucose high criterion defined by Grade 3 and higher events according to CTCAE, Version 4.03, June 14, 2010.

PUBLIC COPY
This document cannot be used to support any marketing authorization application and any extensions or variations thereof.

13.3 Vital sign assessments - abnormal

Abnormality criteria to be applied in the assessment of vital signs parameter values are given below.

PARAMETER	ABNORMALITY CRITERIA
Pulse Rate (beats/minute)	≤ 50 and a decrease from Baseline of ≥ 15 ≥ 120 and an increase from Baseline of ≥ 15
Systolic Blood Pressure (mmHg)	≤ 90 and a decrease from Baseline of ≥ 20 ≥ 180 and an increase from Baseline of ≥ 20
Diastolic Blood Pressure (mmHg)	≤ 50 and a decrease from Baseline of ≥ 15 ≥ 105 and an increase from Baseline of ≥ 15
Temperature	$> 101^{\circ}\text{F}$ (38.3°C)
Body Weight	$\geq 10\%$ decrease from Baseline $\geq 10\%$ increase from Baseline

13.4 Electrocardiogram (ECG) – Abnormal

Abnormality criteria to be applied in the assessment of ECG parameter values are given below:

Parameter	Abnormality Criteria
QT interval (ms)	$\geq 500\text{ms}$
	$\geq 60\text{ms}$ increase from Baseline
QTc(F) (ms)	$\geq 500\text{ms}$
	$\geq 60\text{ms}$ increase from Baseline
PR interval (ms)	Treatment-emergent value $> 200\text{ms}$
QRS interval (ms)	Treatment-emergent value $> 100\text{ms}$
Heart rate (bpm)	$< 50\text{bpm}$
	$> 120\text{bpm}$

Abbreviations: BL= Baseline, bpm = beats per minute; ms = milliseconds; QTc(F) = Fridericia corrected QT interval;

Note: Treatment-emergent is defined as meeting the criteria at any post-Baseline visit during the Treatment Period (including unscheduled visits) and not meeting the same criteria during Baseline

13.5 ITP-PAQ Scoring

13.5.1 ITP-PAQ Scales

Please see below for the items associated for each scale and the number of points in the Likert Scale that will be used per scale where higher numbers mean better health status.

Question	Scale	Response Categories
1	Physical Health: symptoms	0-4
2		
3		
4		
5		
6		
7	Physical Health: fatigue	0-4
8		
9		
10		
11	Physical Health: bother	0-4
12		0-6
13		0-6
14	Physical Health: activity	0-4
15		0-4
16	Emotional Health: psychological	0-4
17		0-4
18		0-4
19		0-4
20		0-4
21	Emotional Health: fear	0-4
22		0-4
23		0-4
24		0-4
25		0-4
26	Overall QoL	0-6
27		0-6
28		0-3
29		0-3
30		0-3
31	Social Activity	0-4
32		0-4
33		0-4
34		0-4
35	Women's reproductive health	0-4
36		0-4
37		0-4
38		0-4
39		0-4
40		0-4
41	Work	0-5
42		0-5
43		0-5
44		0-5

The ITP-PAQ domain scores will be obtained by transforming the raw sum of the item responses to a 0-100 scale. This can be obtained using the following formula:

$$\text{ITP-PAQ score} = \frac{\text{Sum of item scores within the scale}}{\text{raw sum range}} * 100$$

ITP-PAQ domain	Raw sum range
Symptoms	24
Fatigue	16
Bother	16
Activity	8
Psychological health	20
Fear	20
Work	20
Social activity	16
Women's reproductive health	24
Overall Quality of Life	21

Missing data:

A domain score is not calculated if there is more than half of the items of this domain are missing.

If 50% or more of the items are available, missing items are imputed using the mean of non-missing items. For domains that include items with a different number of categories, the imputed response for missing items has to be transformed on the range of the response scale of the missing item.

This document cannot be used to support any marketing authorization application and any extensions or variations thereof.

